13.3.3 Safety endpoints

All participants will be included in all safety analyses. All AEs reported during the study will be included in the analysis. The goal of the statistical evaluation of all AE data will be evaluated using a standardised tabulation of frequency and incidence rates of all observed AEs. The frequencies and incidence rates will be calculated on a per patient basis and not on an even basis.

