10.1.7 Patient daily symptom data

Following randomisation, the process will be explained to participants concerning their documentation of /response to daily SMS regarding any respiratory symptoms. These symptoms and/or condition related to the symptoms will be recorded as adverse events. Unclear or missing entries will be clarified with the participant and any correction annotated by site staff as appropriate. Annotations made by site staff will be clearly identified and initialled and dated.

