10.1.9 Adverse events

[figure not shown]
AEs will be collected from the time the medicinal product is administered. Further information regarding the collection and reporting of AEs can be found in Section 12.

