11.6 Permitted medications during study

During the study, participants will be allowed to take medications routinely used in the management of fever, cough or wheezing attacks, including inhaled and oral steroids. All medications will be recorded in the source documentation and CRF.

12. Assessment of safety

The site investigator is responsible for the assessment and documentation of any event that meets the criteria of an AE (see Section 12.1) or an SAE (see Section 12.2).

AEs and SAEs will be collected from the time of first dose of investigational product until the participant has completed the study at their final visit, even if the participant ceases the investigational product prematurely.

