12.3 Investigator’s responsibility for reporting serious adverse events

All SAEs will be reported within 24 hours of the site staff becoming aware of the event. The SAE (Initial) Form will be completed and faxed to the Sponsor on [contact] using all information known at the time. A minimum of the SAE title, onset date and date the last investigational product was delivered should be provided, and if possible, the form should be reviewed and signed by the site investigator prior to faxing.

Further guidance on SAE reporting, including instructions for completion of the SAE form can be found in Study Reference Manual.

If site staff becomes aware of new information regarding an SAE, a SAE (Follow Up) form should be completed and forwarded to the Sponsor within five days. New information may include recurrent episodes, complications, or progression of the initial SAE, acquisition of relevant hospital records, reports and/or laboratory results. The follow-up information should describe whether the event has resolved or continues, if and how it was treated, and whether the patient continued or withdrew from study participation.

SAEs, regardless of suspected causality, occurring after the patient had provided informed consent and until 30 days after the patient has stopped study participation/ withdrawn, must be reported. Any SAEs experienced after this 30 day period should only be reported if the Investigator suspects a causal relationship to the study drug. SAEs that are ongoing at the end of the study should be followed up until a final assessment is possible, and until all queries from the Sponsor have been resolved.

In accordance with local requirements, the site investigator must also notify their local EC of any SAEs.

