13.2.1 Analysis sample

All participants randomised who receive at least one dose of study treatment will be included in the "intention-to-treat" group for statistical analyses.

Participants who complete the treatment period and take at least 80% of scheduled doses will be included in the "per protocol" group for statistical analyses.

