13.3 Study endpoint assessments

Study endpoint analyses will be conducted 3 months after enrolment and at completion of the study, with an interim analysis planned at month 1.

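### The safety analysis sets no dosing condition, so never-dosed wait-list workers can dilute the treatment-related adverse-event rate, and conflicting collection start points leave the all-cause rate open to error in either direction

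*Combined protocol and SAP*

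**What the plan says.** Section 13.3.3 states "All participants will be included in all safety analyses". It includes every AE reported during the study and adds "The frequencies and incidence rates will be calculated on a per patient basis and not on an even basis" (presumably meaning an event basis). It defines no dosed safety population and no split by arm, period or time on and off OM85. The first safety endpoint, in section 8.2.4, is treatment-related AEs. The safety objective, in section 7.4, is whether giving OM85 to front-line workers is safe.

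The efficacy set in section 13.2.1 does carry a dosing condition: "All participants randomised who receive at least one dose of study treatment will be included". Under section 8.1, Group 1 starts OM85 in Month 3 and Group 2 on Day 0. Under section 9.4, those who leave are not replaced.

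The sections differ on when AE collection starts:

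- Opening of section 12: "AEs and SAEs will be collected from the time of first dose of investigational product".
- Section 10.1.9: "AEs will be collected from the time the medicinal product is administered".
- Section 10.1.7, on the daily SMS symptom reports that follow randomisation in both groups: "These symptoms and/or condition related to the symptoms will be recorded as adverse events". No dose is required.
- Section 12.3 requires reporting of "SAEs, regardless of suspected causality, occurring after the patient had provided informed consent".

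**The concern.** A rate meant to describe the safety of a drug should be taken over people who took it. Here the exposure condition sits on the efficacy set and is missing from the safety set. Anyone in Group 1 who withdraws or declines before Month 3 has no time on OM85 and cannot have an OM85-related event, yet counts as a patient at risk. Group 2 starts on Day 0, so almost all such people are in Group 1, and the two arms' rates would differ for a reason unrelated to the drug.

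The conflicting start points add a second problem. If events before the first dose are recorded for some types of AE and not others, an all-cause table mixes treated and untreated time in a way the reader cannot undo. Both problems bear on the trial's only safety objective.

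**Working it through.** The plan states no AE rate, no AE denominator and no dropout before first dose, so there is no figure of its own to reproduce. The sample-size figures in section 13.2 concern efficacy and do not enter.

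**Inputs**

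- 1000 per arm: 500 in Australia plus 500 in the UK, allocated 1:1 (synopsis).
- r: probability that a dosed worker has at least one post-dose (or treatment-related) AE. Assumed 10%.
- d: fraction of Group 1 never dosed. Not stated; range 0% to 30% assumed.
- All of Group 2 is dosed. Assumed, since treatment starts on Day 0.

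**Step 1. Treatment-related or post-dose AEs**

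Group 1 rate = r × 1000(1-d) / 1000 = r(1-d).

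Pooled rate = [1000r + 1000r(1-d)] / 2000 = r(1-d/2).

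At d = 10%, 900 of Group 1 are dosed and 90 have an event: 90/1000 = 9.0%. Pooled: (100 + 90)/2000 = 9.5%.

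| d | Group 1 | Pooled | Dosed participants only |
|---|---|---|---|
| 0% | 10.0% | 10.0% | 10.0% |
| 5% | 9.5% | 9.75% | 10.0% |
| 10% | 9.0% | 9.5% | 10.0% |
| 20% | 8.0% | 9.0% | 10.0% |
| 30% | 7.0% | 8.5% | 10.0% |

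The relative understatement is d in Group 1 and d/2 pooled, whatever the value of r. Group 2 tabulated alone stays at r.

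**Step 2. All-cause AEs**

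Suppose pre-dose events are also counted, as sections 10.1.7 and 12.3 imply for some of them. Let q be the chance of at least one pre-dose AE, taken as independent of post-dose AEs and equal for those who leave and those who stay. Then

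Group 1 any-AE rate = dq + (1-d)[1 - (1-q)(1-r)].

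With r = 10%, d = 10% and q = 5% (all assumed): 0.10 × 0.05 + 0.90 × (1 - 0.95 × 0.90) = 0.005 + 0.1305 = 13.55%, above the on-drug 10%. With q = 0 the formula returns the 9.0% of Step 1.

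At the same r and d it simplifies to 0.09 + 0.91q, which equals 10% at q = 0.01/0.91, about 1.1%. A small pre-dose event rate is enough to turn dilution into inflation.

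**The case against.** The strongest reply is that the documents do allow AEs to be captured without a dose. Besides sections 10.1.7 and 12.3, section 10.2 and Appendix 1 give Group 1 an AE assessment at Visit 2, where drug is first dispensed, and at any unscheduled visit. Section 10.3 asks those who leave between visits to complete the next visit's procedures. This stands. A reader might infer from section 12 alone that nothing is collected from undosed workers; the other sections contradict that. It also means that an unconditional claim of understatement fails for all-cause AEs. It does not rescue the treatment-related endpoint, because an undosed worker cannot have an OM85-related event however early collection starts.

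A second reply concerns size. Section 13.3 says "Study endpoint analyses will be conducted 3 months after enrolment", when no wait-list worker has yet been dosed under the planned schedule. A reader might infer that the AE rate would then be halved, with 1000 dosed among 2000. That needs a safety table pooled across arms at Month 3, and the plan does not specify one. The analyses detailed for that time concern the primary outcome, and the one safety presentation described, to the DSMB in section 8.3, is by group. By group at Month 3, Group 1 is simply an untreated arm. The halving should not be claimed.

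Third, all of Group 1 is scheduled to receive OM85, so the final analysis is affected only by those lost before Month 3, and the plan does not say how many to expect. This too stands: the effect could be small, and it is nil if nobody is lost.

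**Conclusion.** The point holds in a limited form. Read as written, section 13.3.3 puts never-dosed workers in the denominator of an endpoint to which they cannot contribute. The treatment-related or post-dose rate is then too low by a relative d in Group 1 and d/2 pooled: for an assumed 10% rate, 9.0% and 9.5% at d = 10%, with no effect at d = 0. This assumes that all of Group 2 is dosed; in that case the Group 2 rate, tabulated by group, is correct.

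For all-cause AEs the documents fix neither the direction nor the size, because they give different starts for collection. The figure of 13.55% against 10% shows only that inflation is possible under the assumed inputs.

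The primary efficacy analysis is not touched by this point. The one-dose condition on the set called intention-to-treat is a separate matter. The change should be made before any safety data are tabulated.

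**What to change.** In section 13.3.3, replace the all-participants sentence with wording such as: *AE frequency and incidence on OM85 will be calculated in participants who took at least one dose, counting events from first dose. Participants never dosed are excluded from that denominator and listed separately. Wait-list time before first dose is tabulated separately as untreated.*

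Also reconcile sections 10.1.7, 10.1.9, 12 (opening) and 12.3 to one stated start for AE and SAE collection. Until that is done, the untreated wait-list period cannot serve as a safety comparator, because its events would be collected under a different rule from those on OM85.

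The first change is wording in the analysis section; its downside is a smaller denominator and a slightly less favourable AE rate. The second goes beyond the analysis section. It amends the protocol's collection rules and, depending on the start chosen, may change what sites record for Group 1 before Month 3.

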13.4 Reporting deviations from the original statistical plan

Any deviations from the statistical analysis plan will be described and a justification given in the final clinical study report.

14. Direct access to source data/documents

It is the responsibility of the site investigator to maintain adequate and accurate source documentation to record all observations and other data pertinent to the study. All CRFs should be completed in their entirety to ensure accurate interpretation of the data.

The Investigator's Study Site File should include, but not limited to, approved Protocols and any subsequent Amendments, staff curricula vitae, sample Patient Information and Consent Forms, and other appropriate documents and correspondence used for the study.

14.1 Identification of source data

Data entered into the CRF should be consistent with and substantiated by original source documentation. Source documentation should be legible, complete and attributable to an originator.

14.2 Direct access to source data

The study sites will maintain the highest degree of confidentiality permitted for the clinical and research information obtained from the participants in this study. All medical and research records will be maintained in the strictest confidence. However, as a part of the quality assurance and legal responsibilities of any study, the sites must permit authorised representative of the Sponsor and health authorities to examine (and when required by applicable law) to copy clinical records for the purpose of quality assurance reviews, audits, and evaluations of the study safety and progress.

14.3 Case report forms

Study data will be captured in a Case Report Form (CRF). Each participant will have their own CRF. All participant study records will be completed by site study staff in a timely manner.

Throughout the study the site may receive queries from the monitor to clarify discrepancies or request further data. It is important for the data validation process of the study that all queries are resolved in a timely manner and completed as accurately as possible.

15. Quality control and quality assurance

The site investigator must retain all study records in a secure facility for 15 years after the study closes. Approval to destroy a study-specific documentation should be obtained from the Sponsor prior to the destruction of any study records.

15.1 Study monitoring

The Sponsor monitor (or designee) will regularly inspect the various records of the study, including source documents, CRFs and other pertinent documents.

The monitor will confirm the completeness, consistency, and accuracy of all documented data and verify that all study activities are carried out by the appropriate designated staff. The average monitoring frequency will be determined according to the rate of participant recruitment. In accordance with Good Clinical Practice, the monitor will visit the study site frequently enough to assure that the facilities used by the site investigator continue to be acceptable for the purposes of the study as well as tracking that the study protocol is being adhered to and has been approved by the EC.

15.2 Information to study personnel

It is the investigator's responsibility to ensure that all study personnel who are listed on the Site Responsibility Log receive training on the protocol and are qualified to carry out their delegated study tasks. Evidence of training on the study protocol must be provided for any new personnel that become involved in the study after site initiation has taken place.

It is the monitor's responsibility for initiating the site, ensuring that all study procedures are adhered to according to the approved protocol and for closing out the site at the end of the study.

15.3 Termination of study

The Sponsor reserves the right to terminate the study at any time. If the study is terminated for any reason, the Sponsor will promptly inform the site investigator. The site investigator should provide appropriate follow-up and/or therapy for their study participants. Site investigators should inform their local EC.

15.4 Protocol amendments, violations and deviations

The protocol may be amended by the Sponsor if there are changes that may significantly affect the safety of the participants, scope of the investigation, or the scientific quality of the study. Any protocol amendments must be signed by the site investigator. It must also be submitted to the local EC, with any changes from the final approved protocol not initiated at the study site until appropriate written approval is received by the EC, except when necessary to eliminate an immediate safety risk to the participants, or when the change only involves logistics or administration.

A protocol violation is any failure to comply with the final study protocol as approved by the EC. This includes but is not limited to, the final detailed protocol, patient information and consent form, questionnaires, and other study-related documents. Circumstances which may impact participant safety, affect the integrity of the study data and/or affect a participant's

willingness to participate in the study may be deemed as protocol violations. All protocol violations must be immediately reported to the Sponsor as well as the local EC in accordance with local regulations. A protocol violation page must also be completed.

A protocol deviation involves any modification or alteration to the final study protocol as approved by the EC, but does not fulfil the criteria above for a protocol violation. Examples of protocol deviations may include inappropriate documentation of the informed consent document, implementation of unapproved recruitment procedures, study visits outside of set windows and missing tests and/or laboratory values. All deviations from the protocol and the reason for the deviation will be documented in the source documentation.

15.5 Data safety monitoring board

Prior to the start of the study a DSMB will be assembled consisting of appropriate clinical and statistical experts who are independent of the conduct of the study. The DSMB will provide an ongoing independent review of data from the study to address any safety concerns. The DSMB will review whether the study data are properly collected, analysed and reported. The DSMB will review blinded study results at regular intervals, but may also request unscheduled analysis or additional analysis during the course of the study. They will evaluate periodic assessments of data quality and timeliness, as well as details such as participant recruitment, accrual and retention. The DSMB will make recommendations concerning the continuation or conclusion of the study and will notify the Sponsor accordingly.

15.6 Audits and inspections

All source documents for this study must be made available to staff from the Sponsor or its designees or to health authority inspectors after the appropriate notification. The verification of CRF data will be by direct inspection of source documents.

16. Ethics

16.1 Statement of compliance

This study will be conducted in compliance with the criteria specified in this study protocol, the ethical principles stated in the current revision of the “Declaration of Helsinki”, the International Conference on Harmonization Good Clinical Practice E6 (ICH-GCP) or with the laws and regulations of the country in which the research is conducted, whichever represents the greater protection of the individual.

16.2 Informed consent form

The informed consent form is a means of providing information about the study to a prospective participant and allows for an informed decision about participation in the study. In accordance with GCP, informed consent remains an ongoing process throughout the study.

It is the responsibility of the site investigator, or a person designated by the site investigator (if acceptable by local regulations), to obtain written informed consent from each participant after adequate explanation of the study. After ample time to have all their questions answered by the site investigator or designee, the participant must read, sign and date the informed consent form before they may enter the study, take study treatment, or undergo any study-specific procedures.

The site investigator or designee must also explain to the prospective participant that enrolling in the study is entirely voluntary and that he, she or they may withdraw from the study at any time, for any reason.

A copy of the informed consent form will be given to the prospective participant for review.

The informed consent form must be revised whenever important new safety information is available that results in significant changes in the risk/benefit assessment or whenever any new information becomes available that may affect participation in the study. The prospective participant (including those already being treated) should be informed of the new information, given a copy of the updated informed consent form and give their consent to continue their participation in the study.

16.3 Ethics committee

This protocol, informed consent form (including the participant information sheet and any other material provided to the participant) and any advertising material must be approved by the local EC and the appropriate written approvals made available to the Sponsor before the site may begin screening potential participants.

Any modifications made to the protocol or informed consent form after receipt of the EC’s original approval must be submitted by the site investigator to the committee in accordance with local procedures and regulatory requirements. Approval must be awaited before any changes can be implemented, except for changes necessary to eliminate immediate hazards to study participants.

The site investigator will ensure that prior to the initiation of the study, and also whenever subsequent modifications to the protocol and informed consent form are made, that copies of all EC approvals are sent to the Sponsor.

16.4 Participant confidentiality

The site investigator must ensure that a participant's anonymity will be respected throughout the study and that their identities are protected from unauthorised parties. A participant's privacy and confidentiality will be maintained by the assignment of a unique identification number. On participant records and other documents submitted to the Sponsor, participants should not be identified by their names, rather their unique identification number. These numbers will be used to collect, store and report participant information. The site investigator should keep a Subject Enrolment Log showing codes, names and date of birth of the participants. Confidentiality and protection of data will be maintained according to local regulatory requirements.

All information disclosed or provided by the Sponsor, including, but not limited to, the protocol, participant records, and the results obtained during the course of the study, is confidential, prior to the publication of the results.

The site investigator and any person under his/her authority must maintain this confidentiality and must not disclose the information to any third party without the prior written approval of the Sponsor.

17. Administrative procedures

17.1 Curriculum vitae

A current copy of the curriculum vitae describing the experience, qualification and training of each site investigator, pharmacist and study personnel listed on the Site Responsibility Log will be provided to the Sponsor prior to the beginning of the study. Other relevant documentation such as current medical or professional licenses should also be forwarded at the request of the Sponsor.

